Appendix 9. Management of Liver Enzyme Laboratory values

Clinical laboratory investigation is needed for diagnosis and monitoring based of liver involvement in AGS. One-third of individuals with AGS have baseline hepatic involvement (AST/ALT >3 x ULN and GGT>2.5 ULN). Therefore using the Drug Induced Liver Injury Guidance published by the FDA in July 2009 is not applicable. Thus, the following liver enzyme laboratory testing monitoring is proposed:

- Laboratory screening of hepatic function panel and or comprehensive metabolic panel (including AST, ALT, total and direct or conjugated bilirubin, ALK, GGT and albumin) will be tested according to study schedule.
- At baseline, Model for End-Stage Liver Disease (MELD) (in individuals >12 years) and the Pediatric End-Stage Liver Disease (PELD) tools will be used to assess for underlying hepatic dysfunction. Individuals with scores of >15 will prohibit enrollment.
- If an isolated elevation of ALT/AST>1000 U/L is seen, or direct bilirubin elevation >3x ULN, this will result in updated calculation of the MELD or PELD as age appropriate, and individuals with scores of >15 will be considered for drug tapering and cessation as well as referral to a hepatologist.
- If during study, or prior to enrollment, AST/ALT elevations of >5x ULN are seen, this will result in repeating liver enzyme and serum bilirubin tests weekly. Frequency of retesting can decrease to once a month or less if abnormalities stabilize or the investigational product has been discontinued and the patient is asymptomatic.

In addition, the following assessments will be performed:

- Obtaining a history of recent concomitant drug use (including nonprescription medications and herbal and dietary supplement preparations), alcohol use, recreational drug use, and special diets.
- Ruling out acute viral hepatitis types A, B, C, D, and E where clinically indicated; repeating EBV and CMV PCR; autoimmune markers; nonalcoholic steatohepatitis; and biliary tract disease.
- Obtaining a history of exposure to environmental chemical agents (for example, occupational or recreational exposure)
- Consider obtaining gastroenterology or hepatology consultations

PELD_score = 10 * ((0.480 * In(Bilirubin)) + (1.857 * In(INR)) - (0.687 * In(Albumin)) + Listing_age_factor + Growth)

	Input:					
	Female Male					
Age	yr		•			Results:
Weight	kg	1	•			
Height	cm	n	•	Gr	rowth failure	
Albumin	g/d	dL	•		PELD score	
Bilirubin	mg	g/dL	•			
INR						
ception diagnoses	Age at listing or Age at listing le Noncontributor Urea cycle disc Organic aciden Hepatoblastom	ess than one y ry order mia			[Reset form

MELD_score = (Round the following expression to the nearest integer)((9.57 * In(Creatinine/88.4)) + (3.78 * In(Bilirubin/17.1)) + (11.2 * In(INR)) + 6.43) MELDNa_score = MELD_score + ((1 if the following expression is true, 0 if false)(MELD_score > 11)) * ((1.32 * (137 - Serum_Na)) - (0.033 * MELD_score * (137 - Serum_Na))

Appendix 10. Management of Leukocyte associated laboratory testing and IgG

Exclusion criteria specific to leukocytes:

- Neutropenia (absolute neutrophil count [ANC] <500 cells/µL)
- CD4 <250 cell/µl on lymphocyte subset testing (where Absolute CD4 count=Absolute CD3/CD4 count=CD3/CD4 count=CD4 count=Absolute CD3+CD4+ cells)
- Patients not meeting criteria can follow protocols for further diagnosis and management and be reconsidered for enrollment at a later time

Criteria for consideration of drug tapering and discontinuation:

- IF ANC 750<1000, THEN follow CBC Q 2 weeks until ANC≥1000
- IF ANC 500<750, THEN follow CBC weekly until ANC≥1000.
- IF ANC 250<500, repeat within 48h and if persistent, refer to local immunology or infectious disease clinical team to start ID ppx (as per flowchart below) and consider G-CSF. Repeat weekly thereafter until ANC ≥1000.
- IF ANC <250, repeat within 48h and if persistent, refer to local immunology or infectious disease clinical team to start ID ppx (as per flowchart below) and consider G-CSF. Repeat weekly thereafter until ANC ≥1000.
- If <250 persists > 7 days, refer to local immunology or infectious disease clinical team to start G-CSF and continue to repeat weekly.
 - If <250 persists >14 days after starting G-CSF, decrease dose to next dose increment (ie if 2mg tid decrease to 2mg bid) (Appendix 14) and continue to repeat weekly.
 - If <250 persists >14 days after starting G-CSF and dose reduction, taper to stop baricitinib.
- IF ALC 250<500, THEN follow CBC Q 2 weeks until ALC≥500 AND start ID ppx (as per flowchart below).
- IFALC <250, THEN follow CBC weekly until ALC ≥250 AND refer to local immunology or infectious disease clinical team to start ID ppx (as per flowchart below).
- IF ALC <250
 - If <250 persists > 7 days, repeat 1 week later.
 - If <250 persists >14 days, decrease dose to next dose increment (ie if 2mg tid decrease to 2mg bid) (Appendix 14) and continue to repeat 7 days and 14 days later.
 - If <250 persists >14 days after dose reduction, taper to stop baricitinib.

[figure not shown]
Management of immunologic abnormalities

• When these immunologic abnormalities occur, clinical management recommendations below will be shared with the local team in the form of a letter

via email or fax, to enable the clinical team caring for the patient to use these best practices.

- General recommendations for clinical management of immunologic abnormalities are detailed below, however deviations from this approach by the clinician caring for the patient, during the clinical care of this individual, will not be considered a protocol deviation. The investigative team will retain decision making about drug discontinuation based on the above recommendations.
- Specifically, the use of specific prophylactic agents, G-CSF and GM-CSF may be at the clinician's discretion, for example even if the criteria below for neutropenia are not met, based on the child's overall health and any contraindications (renal function or other medications for example).

For management of leukocyte laboratory abnormalities

Antifungal ppx should be with a drug that covers mold: posaconazole, voriconazole, itraconazole, or caspofungin

PJP ppx: First-line bactrim; Second-line: dapsone, atovaquone, or pentamidine

HSV ppx: acyclovir or valacyclovir

Second immunosuppressant = Prednisone equivalent >=0.3mg/kg/day or Prednisone equivalent >10mg daily OR tacrolimus, sirolimus, cyclosporine, cyclophosphamide, mercaptopurine, mycophenolate mofetil, methotrexate (>=30mg/m2/week), a cytokine blocker, or any chemotherapeutic

Appendix 11. Management of Anemia

Exclusion criteria specific to anemia:

- Hemoglobin <7 mg/dL (70 g/L) will not be enrolled
- Hemoglobin <8 mg/dl will be used as a threshold in infants <2 months
- Patients not meeting criteria can follow protocols for further diagnosis and management and be reconsidered for enrollment at a later time

Criteria for consideration of drug tapering and discontinuation:

- Patients who develop a hemoglobin (Hg) of <7gm/dl*, should be transfused PRBCS as per institutional practice and a post transfusion Hg be measured weekly.
- Patients who develop a hemoglobin (Hg) of <7gm/dl* within <4 weeks of the transfusion should taper baricitinib to next dose increment (e.g. 2 mg tid to 2 mg bid) and be transfused PRBCS as per institutional practice and a post transfusion Hg be measured weekly.
- Patients who develop a hemoglobin (Hg) of <7gm/dl* within <4 weeks of the transfusion should taper baricitinib to next dose increment (e.g. 2 mg bid to 1 mg bid) and be transfused PRBCS as per institutional practice and a post transfusion Hg be measured weekly.
- If hemoglobin (Hg) of <7gm/dl* after two dose reductions, baricitinib should be tapered to cessation.
- Patients who develop a hemoglobin <5gm/dl at any time should taper baricitinib to cessation and be removed from protocol therapy*.
- Patients may dose escalate in a stepwise fashion after Hg>8gm/dl for >4 weeks.

* if acute blood loss in the context of GI bleeding, surgery, documented immune mediated hemolysis or anemia or an accident is the cause of the acute anemia, treatment of the underlying cause prior to drug tapering is warranted prior to drug tapering. Hemoglobin <8 mg/dI will be used as a threshold in infants <2 months. For patients who have been taking baricitinib for > 2 weeks and develop >50% drop in hemoglobin from baseline should have following work-up at minimum: CBC, reticulocyte count, LDH, haptoglobin, DAT, C5b-9, review of peripheral blood smear. Consider consultation with pediatric hematologist.

Management of anemia

- When these hematologic abnormalities occur, clinical management recommendations above will be shared with the local team in the form of a letter via email or fax, to enable the clinical team caring for the patient to use these best practices. The investigative team will retain decision making about drug discontinuation based on the above recommendations.
- General recommendations for clinical management of anemia are detailed above, however deviations from this approach by the clinician caring for the patient, during the clinical care of this individual, will not be considered a protocol

deviation. An example, would be the use of a transfusion at a level higher than the above protocol stipulates, felt to be best taking into consideration the overall health of the patient. Specifically, the use of EPO may be at the clinician's discretion. The investigative team will retain decision making about drug discontinuation based on the above recommendations.

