Appendix 12. Management of Thrombocytopenia and Thrombocytosis

Exclusion criteria specific to thrombocytopenia/thrombocytosis:

- Thrombocytopenia (platelets <30,000/µL).
- Patients who are on anticoagulation or having a history of life-threatening bleeding should be excluded if platelet count is <50,000/µL.
- Patients not meeting criteria can follow protocols for further diagnosis and management and be reconsidered for enrollment at a later time.

Criteria for consideration of drug tapering and discontinuation for thrombocytopenia:

- Patients who develop a platelet count of <20,000/ µL ** should be transfused as per institutional practice. Platelets should be rechecked weekly. If bleeding symptoms occur, platelets should be rechecked sooner.
- Patients who develop a platelet count of <20,000/ µL ** within <4 weeks of transfusion should be transfused as per institutional practice and should taper baricitinib to next dose increment (e.g. 2 mg tid to 2 mg bid). Platelets should be rechecked weekly. If bleeding symptoms occur, platelets should be rechecked sooner.
- Patients who develop a platelet count of <20,000/ µL ** after dose reduction should be transfused as per institutional practice and should taper baricitinib to next dose increment (e.g. 2 mg bid to 1 mg bid). Platelets should be rechecked weekly. If bleeding symptoms occur, platelets should be rechecked sooner.
- Patients who develop a platelet count of <20,000/ µL ** after two dose reductions, baricitinib should be tapered to cessation.
- Patients who develop a platelet count <10,000/ µL at any time should taper baricitinib should be tapered to cessation and permanently discontinued.
- Patients may dose escalate in a stepwise fashion after 4 weeks of stability of platelets > 70,000/ μL.
- Patients with a history of non CNS bleeding should taper baricitinib to the next dose increment if platelet count falls below 30,000/ µL and be transfused. Patients with a history of bleeding or taking anticoagulation cannot be dose escalated. If platelet count drops <30,000/ µL at decreased dosing (Appendix 14), baricitinib should be tapered to cessation and permanently discontinued.

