- Patients with a history of CNS bleeding or taking anticoagulation should taper baricitinib to the next dose increment (Appendix 14) if platelet count falls below 50,000/ µL and be transfused. Patients with a history of bleeding or taking anticoagulation cannot be dose escalated. If platelet count drops <50,000/ µL at decreased dosing (Appendix 14), baricitinib should be tapered to cessation and permanently discontinued.

** if documented immune mediated thrombocytopenia is the cause, treatment of the underlying cause prior to drug tapering is warranted prior to drug tapering. For patients who have been taking baricitinib for > 2 weeks and develop >50% drop in platelet count should have following work-up at minimum: CBC, reticulocyte count, LDH, haptoglobin, DAT, C5b-9, review of peripheral blood smear. Consider consultation with pediatric hematologist.

Criteria for consideration of drug tapering and discontinuation for thrombocytosis:

- Patients who do not have a known vasculopathy and who develop a platelet count of >1,000,000/ µL *** should be rechecked < 1 week.
- If platelets remain >1,000,000/ µL ***, they should taper baricitinib to next dose increment (e.g. 2 mg tid to 2 mg bid). Platelets should be rechecked weekly.
- If platelets remain >1,000,000/ µL *** after dose reduction, they should taper baricitinib to next dose increment (e.g. 2 mg bid to 1 mg bid). Platelets should be rechecked weekly.
- If persistent platelets > 1,000,000/ µL *** after >14 days, should taper baricitinib to discontinuation.
- Patients may dose escalate in a stepwise fashion after 4 weeks of stability of platelets <800,000/ µL.
- For individuals with known CNS vasculopathy (e.g. prior strokes, moya moya), take same measures for platelet counts ≥ 800,000/mcL.
- Consider consultation with pediatric hematologist.

***Consider if there is an alternative explanation (such as intercurrent illness as platelets are an acute phase reactant).

Management of Thrombocytopenia and Thrombocytosis

- When these abnormalities occur, clinical management recommendations above will be shared with the local team in the form of a letter via email or fax, to enable the clinical team caring for the patient to use these best practices

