Appendix 13. Cutaneous LE Disease Area and Severity Index (CLASI)

Appendix 14. Dose tapering guidance

The following serves as guidance for dose tapering if necessary due to subject tolerance. If dose tapering is conducted for subject preference, dose tapering may occur more slowly, as needed for subject tolerance.

in two week increment unless resolution of AE requiring tapering * smaller dose increments obtained by pill cutter, until small pill size can be provided to patient where available

Initial dose	Dose decrease 1 #	Dose decrease 2 #	Dose decrease 3 #	Dose decrease 4 #	Dose decrease 5 #
1 mg bid	1 mg am and 0.5 mg* pm	0.5 mg* bid	0.5 mg am	stop	
1 mg tid	1 mg bid	1 mg am and 0.5 mg* pm	0.5 mg* bid	0.5 mg am	stop
1 mg qid	1 mg tid	1 mg bid	1 mg am and 0.5 mg* pm	0.5 mg* bid	stop
2 mg bid	1 mg tid	1 mg bid	1 mg am and 0.5 mg* pm	0.5 mg* bid	stop
2 mg tid	2 mg bid	1 mg * tid	1 mg * bid	0.5 mg* bid	stop
2 mg qid	2 mg tid	2 mg bid	1 mg * tid	1 mg* bid	stop
3 mg bid	2 mg bid	1 mg * tid	1 mg * bid	0.5 mg* bid	stop
3-2-3 mg	2 mg tid	2 mg bid	1 mg * tid	1 mg * bid	stop
3 mg qid	3-2-3-2 mg	2 mg qid	2-1-2-1 mg	1 mg qid	stop
4 mg bid	2 mg tid	2 mg bid	1 mg * tid	1 mg* bid	stop
4-2-4 mg	2 mg* qid	2 mg tid	2 mg bid	1 mg bid	stop
5 mg bid	4 mg bid	2 mg tid	2 mg bid	1 mg bid	stop
4 mg tid	2 mg* qid	2 mg tid	2 mg bid	1 mg bid	stop
6 mg bid	5 mg bid	4 mg bid	2 mg tid	2 mg bid	stop

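### After 2 mg bid, the anaemia and platelet rules give 1 mg bid as the next dose step, but the Appendix 14 rows within reach of two reductions give 1 mg tid

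*Combined protocol and SAP*

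**What the plan says.** Appendix 11 sets out two reductions for recurrent low haemoglobin. The first is "within <4 weeks of the transfusion should taper baricitinib to next dose increment (e.g. 2 mg tid to 2 mg bid"); the second is "within <4 weeks of the transfusion should taper baricitinib to next dose increment (e.g. 2 mg bid to 1 mg bid"). If haemoglobin is still low "after two dose reductions, baricitinib should be tapered to cessation".

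Appendix 12 repeats the second step for thrombocytopenia ("taper baricitinib to next dose increment (e.g. 2 mg bid to 1 mg bid") and for thrombocytosis ("after dose reduction, they should taper baricitinib to next dose increment (e.g. 2 mg bid to 1 mg bid"). The thrombocytopenia rule also ends in cessation after two reductions. The thrombocytosis rule ends differently: it tapers to discontinuation when platelets stay above 1,000,000/µL for more than 14 days.

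The step table is Appendix 14, introduced with "The following serves as guidance for dose tapering if necessary due to subject tolerance". Section 4.8 cites it where it speaks of tapering to the next dosing increment. Section 9.4.2.2.3 cites it for decreases in anaemia. Appendix 12 cites it for patients with a bleeding history or on anticoagulation. Section 8.8 lists Appendices 11, 12 and 14 among those to be followed.

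**The concern.** The examples and the table are meant to be read together, and both show what comes next after a given dose. For the first reduction they agree: 2 mg tid goes to 2 mg bid in both. For the second they do not, for the dose sequence that the examples themselves use.

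In the anaemia and thrombocytopenia rules the second reduction is the last step before cessation. Its size decides how much drug a child with falling haemoglobin or platelets still receives when the team judges whether reduction has failed. The protocol treats the pace of reduction as important: Section 4.8 warns of rebound inflammation after abrupt discontinuation, and Section 9.4.2.1.1 reports neurologic decline after discontinuation. Two investigators who each follow the text could give the same child different doses.

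**Working it through.** The plan states no percentage reduction, so there is no figure to reproduce. The check is daily-dose arithmetic plus a reading of every Appendix 14 row.

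**Size of the step.** Reduction = (dose before − dose after) / dose before.

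- Appendices 11 and 12: 2 mg bid = 4 mg/day; 1 mg bid = 2 mg/day; (4 − 2)/4 = 50%.
- Appendix 14, rows starting at 2 mg bid, 2 mg tid and 3 mg bid: 2 mg bid = 4 mg/day; 1 mg tid = 3 mg/day; (4 − 3)/4 = 25%.

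**Cumulative effect from 2 mg tid (6 mg/day) after two reductions.**

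- Ending at 1 mg bid: (6 − 2)/6 = 66.7%.
- Ending at 1 mg tid: (6 − 3)/6 = 50%.

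**What Appendix 14 does after 2 mg bid.** Ten of its 14 rows pass through 2 mg bid:

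| Row (initial dose) | The step that leaves 2 mg bid is reduction no. | Next step |
|---|---|---|
| 2 mg bid | 1 | 1 mg tid |
| 2 mg tid | 2 | 1 mg tid |
| 3 mg bid | 2 | 1 mg tid |
| 2 mg qid | 3 | 1 mg tid |
| 3-2-3 mg | 3 | 1 mg tid |
| 4 mg bid | 3 | 1 mg tid |
| 4-2-4 mg | 4 | 1 mg bid |
| 5 mg bid | 4 | 1 mg bid |
| 4 mg tid | 4 | 1 mg bid |
| 6 mg bid | 5 | stop |

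Six rows go to 1 mg tid, three to 1 mg bid and one to stop. A rule that allows two reductions reaches only the first three rows, and all three give 1 mg tid. In each of these, 1 mg bid comes one step later.

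**Are these doses in use?** Yes. In Appendix 3, 2 mg tid is the initial dose for 10 to <20 kg and 3 mg bid the initial dose for 20 to <40 kg. In Appendix 4, 2 mg bid appears for 20 to <40 kg (first escalation) and for ≥40 kg (initial).

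**The case against.** The steps in Appendices 11 and 12 are marked as examples, under headings that present them as criteria to consider, and Appendix 14 calls itself guidance. Because Sections 4.8 and 9.4.2.2.3 point to Appendix 14, a reader can take it as the step table and the parentheses as loose illustration. That softens the conflict, but it also confirms that example and table should agree. Nothing says which prevails.

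The practical reach is small. The difference is 1 mg a day, for a patient at 2 mg bid who needs a further reduction. Section 4.4.2 requires documented consultation and agreement on dose changes, Section 4.9 requires DSMB notice within 48 hours of a decrease, and counts are rechecked weekly. In Table 1B, thrombocytopenia reached grade 3 or 4 in 0 of 34 patients, haemoglobin grade 3 in 1 of 35, and thrombocytosis grade 3 in 1 of 34. The documents do not map these grades to the trigger thresholds, so the counts suggest rarity and no more. All of this stands and keeps the point minor.

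Two stronger readings are tempting and are not supported:

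- A reader might infer that Appendix 14 never goes from 2 mg bid to 1 mg bid. It does, in the 4-2-4 mg, 5 mg bid and 4 mg tid rows. Those rows do not rescue the examples, because they reach that step only as the fourth reduction, whereas the examples start at 2 mg tid and make it the second.
- A reader might infer that all three rules stop after two failed reductions. Only anaemia and thrombocytopenia do. Thrombocytosis concerns high platelets and its stop rule is written as persistence beyond 14 days, so there the step mismatch exists but the argument about the last step before a counted stop does not apply.

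**Conclusion.** The contradiction holds, as a minor one. For the sequence that Appendices 11 and 12 use as their example, the next step after 2 mg bid is a 50% cut in those appendices and a 25% cut in Appendix 14. For anaemia and thrombocytopenia, a child who started at 2 mg tid may be on 2 or 3 mg a day when the decision to stop is made, depending on which text is followed. For thrombocytosis the same mismatch applies to the step only. Appendix 14 is also not uniform in what follows 2 mg bid.

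This rests on reading the next increment as the next column of the Appendix 14 row for the patient's initial dose, which is how that table is laid out. The documents do not support a conclusion that either step is wrong or unsafe, and none is drawn. The primary endpoint, sample size and power are unaffected.

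**What to change.** Reconcile the second-reduction examples in Appendix 11 and in both parts of Appendix 12 with the step sequence in Appendix 14, and reconcile the Appendix 14 rows with each other on what follows 2 mg bid. Alternatively, state in Section 4.8 or in each appendix which text governs when they differ. Which step is right is for the sponsor and the clinical team to decide.

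The cost is a wording amendment, with the IRB approval and FDA notification that Section 9.8.7 requires. No change to data collection, sample size or analysis is needed.

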Appendix 12. Management of Thrombocytopenia and Thrombocytosis

Exclusion criteria specific to thrombocytopenia/thrombocytosis:

- Thrombocytopenia (platelets <30,000/µL).
- Patients who are on anticoagulation or having a history of life-threatening bleeding should be excluded if platelet count is <50,000/µL.
- Patients not meeting criteria can follow protocols for further diagnosis and management and be reconsidered for enrollment at a later time.

Criteria for consideration of drug tapering and discontinuation for thrombocytopenia:

- Patients who develop a platelet count of <20,000/ µL ** should be transfused as per institutional practice. Platelets should be rechecked weekly. If bleeding symptoms occur, platelets should be rechecked sooner.
- Patients who develop a platelet count of <20,000/ µL ** within <4 weeks of transfusion should be transfused as per institutional practice and should taper baricitinib to next dose increment (e.g. 2 mg tid to 2 mg bid). Platelets should be rechecked weekly. If bleeding symptoms occur, platelets should be rechecked sooner.
- Patients who develop a platelet count of <20,000/ µL ** after dose reduction should be transfused as per institutional practice and should taper baricitinib to next dose increment (e.g. 2 mg bid to 1 mg bid). Platelets should be rechecked weekly. If bleeding symptoms occur, platelets should be rechecked sooner.
- Patients who develop a platelet count of <20,000/ µL ** after two dose reductions, baricitinib should be tapered to cessation.
- Patients who develop a platelet count <10,000/ µL at any time should taper baricitinib should be tapered to cessation and permanently discontinued.
- Patients may dose escalate in a stepwise fashion after 4 weeks of stability of platelets > 70,000/ μL.
- Patients with a history of non CNS bleeding should taper baricitinib to the next dose increment if platelet count falls below 30,000/ µL and be transfused. Patients with a history of bleeding or taking anticoagulation cannot be dose escalated. If platelet count drops <30,000/ µL at decreased dosing (Appendix 14), baricitinib should be tapered to cessation and permanently discontinued.
- Patients with a history of CNS bleeding or taking anticoagulation should taper baricitinib to the next dose increment (Appendix 14) if platelet count falls below 50,000/ µL and be transfused. Patients with a history of bleeding or taking anticoagulation cannot be dose escalated. If platelet count drops <50,000/ µL at decreased dosing (Appendix 14), baricitinib should be tapered to cessation and permanently discontinued.

** if documented immune mediated thrombocytopenia is the cause, treatment of the underlying cause prior to drug tapering is warranted prior to drug tapering. For patients who have been taking baricitinib for > 2 weeks and develop >50% drop in platelet count should have following work-up at minimum: CBC, reticulocyte count, LDH, haptoglobin, DAT, C5b-9, review of peripheral blood smear. Consider consultation with pediatric hematologist.

Criteria for consideration of drug tapering and discontinuation for thrombocytosis:

- Patients who do not have a known vasculopathy and who develop a platelet count of >1,000,000/ µL *** should be rechecked < 1 week.
- If platelets remain >1,000,000/ µL ***, they should taper baricitinib to next dose increment (e.g. 2 mg tid to 2 mg bid). Platelets should be rechecked weekly.
- If platelets remain >1,000,000/ µL *** after dose reduction, they should taper baricitinib to next dose increment (e.g. 2 mg bid to 1 mg bid). Platelets should be rechecked weekly.
- If persistent platelets > 1,000,000/ µL *** after >14 days, should taper baricitinib to discontinuation.
- Patients may dose escalate in a stepwise fashion after 4 weeks of stability of platelets <800,000/ µL.
- For individuals with known CNS vasculopathy (e.g. prior strokes, moya moya), take same measures for platelet counts ≥ 800,000/mcL.
- Consider consultation with pediatric hematologist.

***Consider if there is an alternative explanation (such as intercurrent illness as platelets are an acute phase reactant).

Management of Thrombocytopenia and Thrombocytosis

- When these abnormalities occur, clinical management recommendations above will be shared with the local team in the form of a letter via email or fax, to enable the clinical team caring for the patient to use these best practices
- General recommendations for clinical management of thrombocytopenia and thrombocytosis are detailed above, however deviations from this approach by the clinician caring for the patient, during the clinical care of this individual, will not be considered a protocol deviation. The investigative team will retain decision making about drug discontinuation based on the above recommendations.

	anatomical location	n that describes	the most severely aff	ected cutaneous	lupus-associated lesion	
	activ		dama			
				9e		
				Scarring/		
Anatomical Location	Erythema	Scale/ Hypertrophy	Dyspigmentation	Atrophy/ Pannicullitis	Anatomical Location	
	D- absent 1- pink; faint erythema 2- red; 3- dark red; purple/violaceous/ crusted/hemorrhagic	0- absent 1- scale 2- verrucous/ hypertrophic	0- absent 1- dyspigmentation	0- absent 1- scarring 2- severely atrophic scarring or panniculitis		
Scalp			11	See below	Scalp	
Ears					Ears	
Nose (incl. malar area)					Nose (incl. malar area)	
Rest of the face					Rest of the face	
V-area neck (frontal)					V-area neck (frontal)	
Post. Neck &/or shoulders					Post. Neck &/or shoulders	
Chest					Chest	
Abdomen					Abdomen	
Back, buttocks					Back, buttocks	
Arms					Arms	
Hands					Hands	
Legs					Legs	Figure 1. The Cutaneous Lup
Feet					Feet	Erythematosus Disease Area
Mucous membrane lesions ((examine if patient confi	ms involvement)	11		tive lesions have resolved ox) 12 months (dyspigmentation	Pennsylvania, copyright 2009
0-absent; 1-lesion or ulceration			score above remains)			
Alopecia Recent Hair loss (within the last 30 days/as re 1-Yes 0-No	eported by patient)		NB: if scar to coexist i	ring and non-se n one lesion, pl	arring aspects seem case score both	
U-NO						
Divide the scalp into four qu occipital is the line connect	uadrants as shown. The ing the highest points o	dividing line betwe f the ear lobe. A qu	en right and left is the mid adrant is considered affec	lline. The dividing line ted if there is a lesion	e between frontal and within the quadrant.	
Alopecia (clinically not obviously scarred)			Scarring of the scalp (udged clinically)		
Alopecia (clinically not obvio			0- absent 3- in one quadrant 4- two quadrants 5- three quadrants 6- affects the whole skull			
Alopecia (clinically not obvio 0- absent 1- diffuse; noninflammatory 2- focal or patchy in one qua 3- focal or patchy in more th			b- affects the whole sk			

[figure not shown]
